**STATISTICAL ANALYSIS PLAN – 01/03/2020**

## **Statistical Analysis Plan**

The number of 80 total patients (40 in each arm) is similar to many studies that have been adequately powered to detect a clinical difference between nerve blocks. For example, Jaegar et al 2013 Volume 38 Issue 6 discovered a significant difference between muscle strength in femoral nerve versus adductor canal block with a total of 54 patients. 80 patients were chosen because we are hoping to achieve a power of 80%. Previous studies have identified mean opioid consumption in patients undergoing VATS procedure and receiving normal paravertebral nerve blocks is approximately 100mg OME. We hope in our experimental group to detect a difference in mean opioid consumption (10% or more ideally). Based on our goal power of the study, we would need a sample size of 32 patients. After surveying the volume of patients undergoing this procedure at our intended site, we deemed that it would be possible to recruit 60 patients for this study in a reasonable period of time. For parametric data we will use a t-test. For non-parametric data we will use a Mann-Whitney U Test. For categorical data we will use a chi-square test. We may use a log regression evaluation if needed. We will use repeated measures ANOVA test to compare repeated measures for each patient. Statistical data will be analyzed using SAS software.

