#### ***Exclusion criteria:***

- \* Cognitive impairment that would not allow effective nerve block placement or gathering information related to the study (ex. pain score).
- \* Contraindications for nerve block placement such as coagulopathy, use of clopidogrel in the past 48hs, patients on dual antiplatelet therapy, infection at the site of puncture, patient refusal, allergy to local anesthetics.
- \* Chronic opiate consumption (>30 OME/day)
- \* Patient expected to be on therapeutic anticoagulation post procedure.
- \* Pregnancy
- \* Comorbid conditions: Any comorbid condition that in the judgment of the anesthesiologist would preclude the patient from any aspect of the study (ex. sepsis, possibly abnormalities of the thoracic spine or paravertebral anatomy such as neoplastic mass occupying the space, empyema, increased intracranial pressure)

**Randomization:** Patients will be randomized 1:1 into one of the study groups. The groups will be defined as Group 1: ESP block; Group 2: PVNB.

The goal is to include 80 patients (40 in each arm).

Before insertion of catheter, ropivacaine 0.5% will be injected incrementally prior aspiration to decrease the risk of intravascular injection every 5ml. The dose will be left at discretion of the

anesthesiologist performing the nerve block, with a volume that would provide effective dermatome coverage and considering the maximum possible dose to avoid local anesthetic toxicity. After administration of LA catheter will then be placed and left 5cm beyond the needle tip.

**Continuous Infusion:** bupivacaine 0.0625% will be started at 6ml/h and will be titrated up to a max of 12ml/h.

**Bolus:** patients will have access to rescue boluses of 3ml every hour, through the catheter with bupivacaine 0.0625% if needed.

All patients will be assessed daily by the acute pain service. Additional pain medication will be available to all patients per standard of care. All patients will have access to acetaminophen 1g every 6hs, ketamine infusion, and opiates as needed to provide adequate analgesia.

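### The SAP ties one 80% power goal to both 80 and 32 patients, calls 60 recruitable, and gives no SD, alpha or dropout, so the power cannot be verified

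*SAP*

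**What the plan says.** The whole sample-size justification is one paragraph of the SAP (Statistical Analysis Plan). In order, it states:

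- **Planned size:** "The number of 80 total patients (40 in each arm) is similar to many studies" that were adequately powered. The one example given had 54 patients and a muscle-strength outcome.
- **Reason for 80:** "80 patients were chosen because we are hoping to achieve a power of 80" percent.
- **Control mean:** opioid consumption in VATS patients "receiving normal paravertebral nerve blocks is approximately 100mg OME".
- **Effect:** a hoped-for difference in mean opioid consumption of at least 10%, which is about 10 mg OME on that mean.
- **Required size:** "Based on our goal power of the study, we would need a sample size of 32 patients".
- **Feasibility:** "we deemed that it would be possible to recruit 60 patients for this study in a reasonable period of time".

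The protocol (Randomization, under Exclusion criteria) also sets the goal at 80, with 40 per arm, and says "Patients will be randomized 1:1 into one of the study groups". It gives no justification for the number.

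Neither document states an SD for opioid consumption, a significance level, one- or two-sided testing, or a dropout allowance. Neither says whether 32 is a total or per arm. The paragraph reads continuously, with no sign of redaction.

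**The concern.** A single power goal for a single effect leads to one required sample size. Here the same 80% goal is attached to two, 80 and 32, and a third number, 60, appears as what the site can supply. The 60 is a feasibility figure and not a power figure. Even so, it is 20 below the target in both documents, and below 64 if 32 means per arm.

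What is at stake is the reading of a null result on opioid consumption. Depending on which sentence reports the real calculation, 60 patients is either ample or underpowered for the 10 mg difference the SAP names. The reader cannot tell which, and cannot confirm that 80 patients give 80% power.

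**Working it through.** **Inputs from the documents.** Difference: 10% × 100 mg = 10 mg OME. Power goal: 80%. Allocation: 1:1. Candidate sizes: 80 total, 32 (total or per arm), 60 recruitable.

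**Inputs not in the documents, assumed here.** Two-sided alpha 0.05, with one-sided 0.05 as a check, and a two-sample t-test. The SAP also allows Mann-Whitney U and does not say which test the size was based on.

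**1. Reproducing the plan's figure.** The usual formula is n per arm = 2 × SD² × (z₁₋α/₂ + z₁₋β)² / difference². Without an SD and alpha it cannot be evaluated, so neither 32 nor 80 can be reproduced. It can be run backwards to find the SD each size would need.

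**2. Implied SD.** By the normal approximation, SD = 10 / [(1.960 + 0.842) × √(2/n)]:

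- 16 per arm (32 total): 10 / (2.802 × 0.3536) = 10.1 mg
- 32 per arm (64 total): 10 / (2.802 × 0.25) = 14.3 mg
- 40 per arm (80 total): 10 / (2.802 × 0.2236) = 16.0 mg

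The noncentral t gives standardized differences of 1.024, 0.711 and 0.634, hence SDs of 9.8, 14.1 and 15.8 mg. These are used below. Because the SDs differ, no single set of inputs makes more than one of these sizes the 80%-power size.

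**3. Power at 60 and 80, by which sentence is taken as the calculation (noncentral t).**

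| Size taken to give 80% power | Implied SD | Power at 60, two-sided | Power at 80, two-sided | Power at 60, one-sided 0.05 |
|---|---|---|---|---|
| 32 total | 9.8 mg | 97% | 99.5% | 96% |
| 32 per arm | 14.1 mg | 77% | 88% | 78% |
| 80 total | 15.8 mg | 68% | 80% | 69% |

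The SD column is two-sided. For the one-sided column each row was solved again for 80% power. The spread at 60 is nearly the same either way.

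**4. Can dropout link the numbers?**

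- 32 total to 80: 1 − 32/80 = 60% loss. 32 total to 60: 1 − 32/60 = 47% loss.
- 32 per arm is 64 evaluable, and 64 / (1 − 0.20) = 80 exactly. The 20% is found in neither document. Under it, 60 recruited leaves 60 × 0.80 = 48 evaluable (24 per arm), with 67% power at a standardized difference of 0.711.

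**5. How much the missing SD matters.** Power for 10 mg, two-sided 0.05, over an assumed SD range:

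| Assumed SD | Power at 60 | Power at 80 |
|---|---|---|
| 10 mg | 97% | 99% |
| 15 mg | 72% | 84% |
| 20 mg | 48% | 60% |
| 30 mg | 25% | 31% |

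At an SD of 20 mg, 80% power for 10 mg needs 128 patients in total. The difference detectable with 80% power at that SD is 0.634 × 20 = 12.7 mg with 80 patients and 0.736 × 20 = 14.7 mg with 60.

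**The case against.** The strongest defence is that 32 is a minimum and 80 a generous margin. Planning 80 against a need of 32 meets an 80% goal, so the sentences could coexist and the fault would be thin documentation. A second reading, 32 per arm with 20% dropout, gives 80 exactly. The 60 is not called a target or a ceiling, and both documents agree on a planned N of 80. Finally, the power figures above rest on an alpha, a test and SDs that the documents do not supply.

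Part of this stands. Neither 32 nor 80 can be shown wrong without an SD, the 60 is only a feasibility estimate, and the SD table shows sensitivity rather than this trial's actual power. The 10 mg is itself soft, since the SAP speaks of hoping for 10% or more on an approximate mean.

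The rest does not clear the point. The SAP gives the 80% goal as the reason for choosing 80. If 32 were the requirement, power at 80 before any dropout would be about 99.5% (32 total) or 88% (32 per arm). The dropout reading depends on a figure found nowhere and puts the recruitable 60 below the 64 it requires. The minimum reading also relies on 32 having been derived correctly, which cannot be checked.

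**Conclusion.** The concern holds and must be fixed. As written, the SAP credits the same 80% power to 80 patients and to 32, leaves the recruitable 60 unreconciled with the target of 80, and omits the inputs needed to decide between them. This is more than missing detail, because the sample sizes and the claimed power disagree within one paragraph. For 10 mg, under the assumed t-test at two-sided 0.05, power at 60 patients is 97%, 77% or 68% depending on which sentence is believed. The review does not conclude that 80 is too few. It concludes that the power at 80, or at 60, is unknown from the documents.

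**What to change.** 1. State whether 32 is per arm or total.
2. Replace the sentences on 80 and on 32 with one calculation, for example:

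> With __ evaluable patients per arm, a two-sided t-test at alpha __ has __% power to detect a 10 mg OME difference (10% of about 100 mg), assuming an SD of __ mg [source]; allowing __% dropout, __ patients will be randomized.

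3. Explain 60 against 80. Either say how 80 will be reached, for instance by a longer recruitment period, or set 60 (30 per arm) in both protocol and SAP.
4. Restate the power, or the difference detectable with 80% power, for the N chosen.

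**Cost.** This is a wording change in the SAP, and in the protocol too if 60 is chosen. The restatement needs no extra patients. The downside is that the stated power may fall. If the SD exceeds about 15.8 mg (two-sided 0.05; about 17.8 mg if one-sided), 80 patients do not give 80% power for 10 mg, and a larger detectable difference has to be declared.

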## **ESP vs. PVB Nerve Blocks for Video Assisted Thoracoscopic Surgery (VATS) Research Protocol**

Continuous paravertebral analgesia and erector spinae plane blockade (ESP) are accepted techniques at UPMC for pain management in thoracic surgery. This is a prospective randomized study intended to assess the efficacy, safety and side-effect profile of continuous ESP block Vs continuous paravertebral block for VATS procedures.

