### **Postoperative period**

- total opioid consumption (in morphine equivalents) and pain scores on the numeric pain rating scale will be documented every 6hs for the first 24hs.
- Incentive spirometer daily score postoperatively
- Length of stay,

- Duration of catheter
- Use of additional pain medication will be recorded
- Document adverse events or complications related to nerve blocks
- dermatome spread with infusion infusion will be documented.

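### Does the SAP need a small-count exception to its chi-square rule for categorical data?

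*SAP*

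**What the plan says.** The Statistical Analysis Plan assigns tests by data type. For categorical outcomes the whole provision is "For categorical data we will use a chi-square test". It gives no expected-count threshold, exact test, continuity correction or significance level. One other sentence could reach binary data, "We may use a log regression evaluation if needed", but it names neither an outcome nor a trigger, so it is not a small-sample rule.

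The protocol's opening section says the study will "assess the efficacy, safety and side-effect profile of continuous ESP block Vs continuous paravertebral block", and the list under Postoperative period includes "Document adverse events or complications related to nerve blocks". Neither document gives an expected complication rate, singles out a complication, or sets a separate analysis for complications. The chi-square rule therefore applies to them only by default.

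On size, the protocol plans 80 patients, 40 per arm, and "Patients will be randomized 1:1 into one of the study groups". The SAP also plans for 80 but later says "we deemed that it would be possible to recruit 60 patients for this study in a reasonable period of time", so 30 per arm is worth checking as well.

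**The concern.** The chi-square p-value is a large-sample approximation, and the customary guide is that every expected cell count should be at least 5. Complications of a nerve block may well be infrequent. If so, most complication tables in a trial of this size would fail that guide, and the plan would be applying the test where textbooks advise against it.

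Two things would be at stake. The first is false alarms on safety, if the true type I error were well above nominal. The second is fragile conclusions. With 6 events against 1 at 40 per arm, Pearson chi-square falls just under 0.05 while Fisher's exact test gives 0.108, so a significance statement about a complication would turn on the choice of test. Because safety is a stated aim, a reader may expect an exact-test fallback.

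**Working it through.** **Inputs.** n = 40 per arm (Protocol, Randomization paragraph), with n = 30 per arm as a check (half of the SAP's 60). The documents give no event rate, so a range is used. Assumed because not stated: two-sided alpha 0.05, the uncorrected Pearson statistic, equal arms and no dropout. The SAP has no figure of its own on this point to reproduce; its 32-patient calculation concerns opioid consumption.

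**1. When do expected counts fall below 5?** Under equal rates, the expected events per arm are n × pooled rate.
- 40 per arm: 5/40 = 12.5%.
- 30 per arm: 5/30 = 16.7%.

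The guide is therefore broken at any lower pooled rate.

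**2. Does breaking it inflate type I error?** With a and b events in arms of size n, and m = a + b,

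X² = 2n(an − bn)² / [n² · m · (2n − m)].

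The true error at a common rate p is the sum, over all (a, b) that the test rejects, of Bin(a; n, p) × Bin(b; n, p).

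| Common rate | Pearson, 40/arm | Fisher, 40/arm | Pearson, 30/arm |
|---|---|---|---|
| 1% | 0.1% | 0.0% | 0.0% |
| 2% | 0.7% | 0.0% | 0.3% |
| 5% | 4.3% | 0.4% | 2.8% |
| 10% | 5.9% | 1.7% | 5.4% |
| 12.5% | 5.6% | 2.2% | 5.5% |
| Maximum over all rates | 5.90% (at 9.2%) | 3.3% (at 50%) | 5.54% (at 11.6%) |

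At 40 per arm the worst excess is 5.9 − 5.0 = 0.9 percentage points. At rates of 5% or lower the test is conservative. If an analyst applied the Yates correction instead, the error at 40 per arm would never exceed 3.3%, so neither reading of the SAP gives a seriously liberal test.

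**3. Single tables.** At 40 per arm:
- 6 against 1: X² = 80 × (6×40 − 1×40)² / (40² × 7 × 73) = 3,200,000 / 817,600 = 3.91, p = 0.048. Barnard 0.059, Boschloo 0.070, Fisher 0.108.
- 4 against 0: X² = 80 × (160)² / (40² × 4 × 76) = 2,048,000 / 486,400 = 4.21, p = 0.040. Barnard 0.043, Boschloo 0.082, Fisher 0.116.

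The tests differ, but the exact tests also differ among themselves. In the second table Barnard's exact test sides with Pearson.

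**4. What would a fallback buy?** Take the usual rule: Pearson if all expected counts are at least 5, otherwise Fisher.
- Type I error at 40 per arm: 0.4% at a 5% rate, 2.6% at 10%, 5.0% at 20%. The maximum over all rates is 5.67%, at a rate of 50%, where Pearson is still the test in use. Against 5.90%, the gain in the maximum is 0.23 points.
- Power, Pearson against the fallback rule:

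| True rates | 40/arm | 30/arm |
|---|---|---|
| 20% vs 5% | 57% → 48% | 45% → 27% |
| 10% vs 1% | 44% → 15% | 28% → 6% |

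**The case for a change.** The strongest reply is that average error hides unevenness. Conditional on the total number of events at 40 per arm, Pearson's error is 0% with 1 to 3 events, 11.6% with 4 (2 × 91,390 / 1,581,580, the chance that all four fall in one arm), 5.5% with 5, 2.6% with 6 and 10.8% with 7. Someone who holds that inference should condition on the events seen would call 11.6% too high and want Fisher's test. That is a respectable position. It is also a long-standing disagreement between sound approaches, and the high values are offset by the zeros and low values beside them. Judged over repeated trials, the error stays near 5% or below.

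A second reply is that the gap invites a choice of test after the counts are known. It has limited force, because the SAP names one test for all categorical data and Fisher, Barnard and Boschloo are not on offer. What is open is the continuity correction and alpha. Read plainly, a chi-square test means the uncorrected Pearson form, and 5% two-sided is the usual default. An analyst would supply both without controversy, though stating them would be tidier.

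A third reply is that a non-significant comparison of rare events says little about equal safety. That is true: zero events in 40 still allows a true rate of up to 8.8% (11.6% for zero in 30). But it limits what any test can show at this size, and Fisher's lower power would make it worse. Giving counts per arm with an interval is good reporting practice and is compatible with the SAP as it stands.

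**Conclusion.** The observation is accurate: there is one rule for categorical data, it has no exception for sparse tables, and expected counts fall below 5 at pooled rates under 12.5% with 40 per arm. It does not show that the rule is wrong. Under the planned test the type I error is at most 5.9% (5.5% at 30 per arm), and it is below nominal at rates of 5% or lower. Switching to Fisher's test for sparse tables lowers the maximum by 0.23 points. At 40 per arm it costs 9 to 29 percentage points of power in the two scenarios examined, in a comparison whose purpose is to notice harm. Keeping chi-square is a fair trade-off.

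This rests on alpha 0.05 two-sided, the uncorrected statistic, full recruitment and assumed event rates, since the documents give none. The data concerned are secondary, with no complication-specific test planned, and the opioid-consumption comparison that drives the sample size is unaffected. Following the SAP as written would give sound results on this point, so no change is called for.

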## **Data collection**

### ***Preoperative period:***

In addition, to treat breakthrough pain, all patients will receive multimodal analgesia per routine.

An excel sheet will be available to collect the patient information from EMR and the patient.

- Data to be collected: age, gender, type of surgery, type of anesthesia (including medications and type regional anesthesia received).
- Incentive spirometer baseline measure prior to surgery
- dermatomal spread (pinprick and or changes in temperature (cold or hot) sensation) after 15-20mins of initial bolus will be documented.

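### The SAP does not say how baseline spirometry is used; making it a covariate would sharpen the spirometry comparison at almost no cost

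*SAP*

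**What the plan says.** The protocol collects spirometry at two stages. Under Data collection, Preoperative period, it lists "Incentive spirometer baseline measure prior to surgery". Under Postoperative period it lists "Incentive spirometer daily score postoperatively", with no number of days. In the same list, opioid use and pain scores do have a window: they "will be documented every 6hs for the first 24hs".

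The Statistical Analysis Plan is a single paragraph that mentions neither spirometry nor a baseline value. For continuous data it says "For parametric data we will use a t-test", with a Mann-Whitney test as the non-parametric alternative. For serial data it says "We will use repeated measures ANOVA test to compare repeated measures for each patient". The only regression is "We may use a log regression evaluation if needed", with no outcome or covariates given. Allocation is simple to describe: "Patients will be randomized 1:1 into one of the study groups".

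**The concern.** A preoperative reading of the same quantity usually predicts the postoperative one, and this trial already collects it. The SAP leaves an analyst three ways to proceed, and they do not give the same precision:

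- **Ignore baseline.** The comparison is unbiased, but between-patient variation that baseline could explain stays in the error term.
- **Enter baseline as a time level and read the arm-by-time contrast.** This behaves like a change score, which is noisy when the correlation is modest.
- **Enter baseline as a time level and read the arm main effect.** Randomisation makes the expected arm difference at baseline zero, so with k postoperative days the effect is diluted to k/(k+1) of its true size.

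What is at stake is the width of the confidence interval for spirometry, plus an analysis choice left open until the data are in. Bias, type I error and the opioid outcome behind the sample size are not at stake.

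**Working it through.** **Inputs from the documents.** 40 per arm (protocol, Randomization paragraph), or 30 per arm if only the 60 patients the SAP thinks recruitable are enrolled ("it would be possible to recruit 60 patients for this study"). The SAP gives no spirometry calculation to reproduce; its figure of 32 patients concerns opioid consumption.

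**Assumptions, none given in the documents.** Baseline-to-postoperative correlation r from 0.3 to 0.8; equal SDs before and after surgery unless stated; true effect 0.5 SD unless stated; two-sided 5% test. Power is from the noncentral t distribution with 2n−2 degrees of freedom (2n−3 for ANCOVA).

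**Single postoperative day.** Variances relative to the postoperative-only comparison:

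- change score: 2(1−r)
- ANCOVA: 1−r²

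The reduction in interval width is 1 − √(ANCOVA variance / smaller of the other two). At r = 0.5 this is 1 − √(0.75/1.00) = 13%; at r = 0.7 it is 1 − √(0.51/0.60) = 8%.

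| r | 0.3 | 0.5 | 0.6 | 0.7 | 0.8 |
|---|---|---|---|---|---|
| Change variance | 1.40 | 1.00 | 0.80 | 0.60 | 0.40 |
| ANCOVA variance | 0.91 | 0.75 | 0.64 | 0.51 | 0.36 |
| CI narrower than better alternative | 5% | 13% | 11% | 8% | 5% |
| Power, 40/arm: postoperative-only | 59.8% | 59.8% | 59.8% | 59.8% | 59.8% |
| Power, 40/arm: change | 46.3% | 59.8% | 69.5% | 81.4% | 93.7% |
| Power, 40/arm: ANCOVA | 63.9% | 72.2% | 78.8% | 87.1% | 95.7% |
| Gain over better alternative (points) | 4.0 | 12.4 | 9.3 | 5.8 | 2.0 |

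At 30 per arm the gains are about 4/12/10/7/3 points.

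**Mean of three postoperative days** (the number is assumed; one common correlation r between all readings). Variances:

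- postoperative mean: (1+2r)/3
- change contrast: (1+2r)/3 + 1 − 2r
- ANCOVA: (1+2r)/3 − r²

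At r = 0.5 these are 0.667, 0.667 and 0.417.

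| r | 0.3 | 0.5 | 0.6 | 0.7 | 0.8 |
|---|---|---|---|---|---|
| Power, 40/arm: postoperative mean | 85.6% | 77.2% | 73.2% | 69.5% | 66.0% |
| Power, 40/arm: change contrast | 62.8% | 77.2% | 85.6% | 93.7% | 99.0% |
| Power, 40/arm: ANCOVA | 91.2% | 92.8% | 95.1% | 97.8% | 99.6% |
| Gain, 40/arm (points) | 5.6 | 15.6 | 9.5 | 4.0 | 0.7 |
| Gain, 30/arm (points) | 7.4 | 19.4 | 13.5 | 7.4 | 2.1 |

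If the diluted arm main effect were read instead (effect 0.5 × 3/4 = 0.375, variance (1+3r)/4), power at 40 per arm would be 67/55/51/47/44%.

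**Unequal SDs.** Change variance minus ANCOVA variance equals (SD_pre − r × SD_post)², so the two tie only when SD_pre = r × SD_post. For a single day at 40 per arm, the gain over the better alternative is about 0 to 5 points when SD_pre/SD_post = 0.8 and about 4 to 19 points when it is 1.25.

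**Cost of the covariate.** Estimating the slope multiplies the ANCOVA variance by about 1 + 1/(N−4): 1.013 at N = 80 and 1.018 at N = 60. The tables leave this factor out; including it trims the gains by less than 1 point. In the worst case, r = 0, single-day power falls by about 0.6 points (N = 80) or 0.7 points (N = 60). ANCOVA breaks even with the postoperative-only comparison at r of about 0.12 to 0.14.

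**Simulation.** With two postoperative days, r = 0.5 and 40 per arm, simulated power was 72% postoperative-only, 72% change, 44% main effect with baseline as a level, and 87% ANCOVA.

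**The case against.** The strongest reply is that an unadjusted analysis of a randomised comparison is valid, so ANCOVA is an efficiency preference, and spirometry is one item in a data-collection list that no document ranks as primary or secondary. That is right, and it is why the point is minor.

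The SAP is also silent rather than exclusionary. A preoperative reading followed by daily ones could naturally go into the repeated measures ANOVA with baseline as the first level. The natural test would then be the arm-by-time contrast, so the 44 to 67% power for the main effect is not a fair measure of the problem. This is accepted: the gains above are measured against the better of postoperative-only and change, not against the main effect.

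The power gains also depend on the assumed effect. For a single day at 40 per arm, over r = 0.3/0.5/0.6/0.7/0.8, they are:

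- effect 0.2 SD: 0.9/3.2/3.0/2.8/2.6 points
- effect 0.3 SD: 2.1/7.1/6.4/5.7/4.4 points
- effect 0.8 SD: 1.7/4.1/1.6/0.3/0.0 points

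With three days and 0.8 SD the gain is at most 0.9 points. The largest gains arise at r = 0.5, exactly where the two simpler analyses tie when SDs are equal. This stands as a caution on the power figures. The narrowing of the interval does not depend on the effect size and is the better summary.

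Finally, the missing definition of the spirometry days may be a larger gap than the missing covariate. Both can be closed in the same sentences.

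**Conclusion.** The point holds, as a minor one. The SAP states no role for a baseline value the protocol already collects, and the tests it names do not use that value in the most precise way. With equal SDs and r between 0.3 and 0.8, covariate adjustment narrows the single-day interval by about 5 to 13% against the better simpler analysis. The power this buys ranges from almost nothing to 12 points for one day at 40 per arm across effects of 0.2 to 0.8 SD. It can be larger if several days are averaged or if baseline is more variable than the postoperative reading. The correlation, SDs, effect size and number of days are all assumptions. That ANCOVA is asymptotically at least as precise as the alternatives does not depend on them, and the finite-sample penalty if baseline proves uninformative is under 1 point of power.

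**What to change.** Add one or two sentences to the Statistical Analysis Plan that:

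- name the postoperative day or days on which spirometry is compared, since none is set and readings may stop at discharge;
- specify either ANCOVA on one prespecified day, or a longitudinal mixed model of postoperative days only (arm, day, arm-by-day), with preoperative spirometry as a covariate in either case;
- state the rule for patients with no baseline reading;
- commit to reporting the adjusted arm difference with its 95% confidence interval.

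The cost is this text and about one degree of freedom. It needs no new data, visits or patients, and leaves the opioid-based sample size as it is.

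### If the planned repeated measures ANOVA is applied complete-case to daily spirometry, patients discharged early are dropped and the arm difference can be biased in either direction

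*SAP*

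**What the plan says.** The SAP gives one sentence to repeated outcomes: "We will use repeated measures ANOVA test to compare repeated measures for each patient". It does not say which outcomes this covers, which days enter, which SAS procedure is meant, or what happens to a patient with some values missing.

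The Protocol has two kinds of repeated postoperative outcome (Postoperative period). Opioid use and pain scores have a fixed window: they "will be documented every 6hs for the first 24hs". Spirometry has none: "Incentive spirometer daily score postoperatively", with no last day. The same list contains "Length of stay", so discharge time is expected to vary. No spirometry after discharge and no discharge criteria are described. Before surgery the Protocol also collects "Incentive spirometer baseline measure prior to surgery"; the SAP states no use for it.

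The sample-size reasoning concerns another outcome: "We hope in our experimental group to detect a difference in mean opioid consumption".

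**The concern.** Classical repeated measures ANOVA needs every time point for every patient. Applied to daily spirometry over several days, it would keep only patients who stayed to the last analysed day. That subset is formed after randomisation.

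Two conditions are needed for bias. First, discharge must be related to the score, which is plausible for a measure of recovery but is not documented. Second, recovery or the discharge rule must differ by arm. If both hold, the patients kept in the two arms are no longer comparable, and the spirometry result can be too small, too large or spurious. If either fails, the cost is lost precision.

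**Working it through.** The plan gives no spirometry figure to reproduce; its power statements concern opioid consumption. The check therefore shows what complete-case analysis does under stated assumptions.

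**Inputs.** From the documents: 1:1 allocation, 40 per arm (Protocol), one baseline value, one score per day. Assumed: scores with SD 1, correlation 0.7 between any two occasions including baseline, three postoperative days, day 1 always recorded. A patient leaves before the next day once today's score exceeds a threshold c, except that a share s stays whatever the score.

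**Step 1: two days, by formula.** Let μ be the arm mean, and φ and Φ the normal density and distribution function. Among patients kept to day 2, the day 1 mean is shifted down by

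k = (1 − s)·φ(c − μ) / [s + (1 − s)·Φ(c − μ)],

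and the day 2 mean by 0.7k. The error in the two-day arm difference (B minus A) is 0.85·(k_A − k_B), where 0.85 = (1 + 0.7)/2.

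- *Common rule, c = 1, s = 0, true difference 0.50.* k_A = 0.2420/0.8413 = 0.2876; k_B = 0.3521/0.6915 = 0.5092. Error 0.85 × (−0.2216) = −0.188, so 0.50 appears as 0.31.
- *Common rule, no true difference.* k_A = k_B, so the error is 0.
- *No true difference, c = 1 in A and 0.5 in B.* The same two k values apply, so −0.19 appears where the truth is 0.
- *Common rule, c = −0.5, s = 0.30, true difference 0.50.* k_A = 0.7 × 0.3521/(0.3 + 0.7 × 0.3085) = 0.478; k_B = 0.7 × 0.2420/(0.3 + 0.7 × 0.1587) = 0.412. Error 0.85 × 0.066 = +0.056, so 0.50 appears as 0.56.
- *Discharge unrelated to the score.* Both shifts are 0, so there is no error.

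The first and fourth cases have opposite signs under a common rule, so the direction depends on the mechanism.

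**Step 2: three days, by simulation.** Complete-case arm difference in the three-day mean, in SD units:

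| Assumed mechanism | Truth | Complete-case | With baseline |
|---|---|---|---|
| Sharp common threshold 1.5 / 1.0 / 0.6 (about 66 / 54 / 41 of 80 complete) | 0.50 | 0.34 / 0.27 / 0.22 | 0.42 / 0.38 / 0.34 |
| Same thresholds, 30-50% stay regardless | 0.50 | 0.39 to 0.46 | – |
| Threshold 0 or −0.5, 30-50% stay regardless | 0.50 | 0.52 to 0.62 | – |
| Logistic discharge, common rule, slope 0.5 / 1 / 2 on the last score | 0.50 | 0.468 / 0.401 / 0.305 | – |
| Threshold 1.5 / 1.0 / 0.6, but 0.5 SD lower in one arm | 0 | −0.16 / −0.23 / −0.28 | −0.08 / −0.13 / −0.16 |
| Logistic, intercept differing by arm, slope 0.5 / 1 / 2 | 0 | −0.13 / −0.20 / −0.20 | – |
| Discharge unrelated to score, 40% v 80% complete | 0.50 | 0.50 | 0.50 (0.505) |
| Sharp common threshold | 0 | 0.00 | – |

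The logistic rows use scores rising 0.3 SD per day. Without baseline, the false-positive rate is 15%, 23% and 30% in the arm-specific threshold row, 11% and 13% in the arm-specific logistic row (slopes 1 and 2), and 5% in the last row.

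**Step 3: using all observed values.** Selection on the day 1 score leaves the regression of day 2 on day 1 unchanged. In the first case of Step 1, the day 2 mean of the patients kept in arm B is 0.5 − 0.7 × 0.5092 = 0.1436. Their day 1 mean is 0.5092 below the full arm's, so adding back 0.7 × 0.5092 = 0.3564 gives 0.500, the true mean. In simulation, the baseline-adjusted mixed model on days 1-2 gives 0.50 under the sharp common thresholds (power 91-95%) and 0.00 in the arm-specific threshold row. Day 1 alone, adjusted for baseline, also gives 0.50 and 0.00, with 86% power.

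**Step 4: like for like.** Complete-case on days 1-2 with baseline gives 0.44 / 0.40 / 0.37 under the sharp common thresholds. Of the gain over the three-day unadjusted analysis (0.16 / 0.23 / 0.28), the shorter window and baseline adjustment supply 0.10 / 0.13 / 0.15. Keeping incomplete patients supplies the remaining 0.06 / 0.10 / 0.13.

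**The case against.** The strongest reply is that the plan states no error. The harm needs a chain of conditions, none of them written down: the ANOVA is used for spirometry, it is run complete-case, the analysed days extend past discharges, discharge depends on the score, and recovery or the rule differs by arm. The ANOVA may be meant for the six-hourly opioid and pain data, which are little exposed, and the SAP's sentence does not exclude a likelihood fit that keeps all values. This stands, and it is why the point is conditional. It does not remove the point, because the SAP does not exclude the harmful reading either.

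A reader might infer that dropping early leavers always hides a benefit. That is not supported: the result rests on the assumed cutoff, and the sign reverses when enough patients stay regardless of score. There is also a narrow case with no bias at all: normal scores of equal variance, with a log-linear chance of staying.

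An arm-specific discharge rule is speculative. Both arms have the same infusion, daily pain-service assessment and access to additional analgesia. The available text describes neither discharge criteria nor blinding, so such a rule cannot be excluded, but nothing suggests it.

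A reader might also infer that the SAP rejects baseline adjustment. It names no covariates for any outcome, so it is silent on the matter. Finally, baseline-adjusted complete-case analysis over three days has 91% power at the mildest sharp threshold, above the 86% of the single-day option; its estimate there is still 0.42 for a true 0.50.

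**Conclusion.** The concern holds as a conditional risk for spirometry. If the ANOVA is run complete-case on daily scores, the arm difference can be biased when discharge is related to the score and either recovery or the discharge rule differs by arm. Otherwise the loss is precision only.

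Neither size nor direction can be derived from the documents, which give no spirometry SD, correlation, length-of-stay distribution or discharge rule. At the assumed correlation of 0.7 over three days, a true 0.50 SD appears anywhere from about 0.22 to 0.62 SD under a common rule, and close to 0.50 when the link to the score is weak. A spurious −0.13 to −0.28 SD appears under an assumed arm-specific rule.

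The documents do not support the stronger readings that the SAP has chosen to discard incomplete patients, or that its opioid comparison is compromised: opioid and pain data have a fixed 24-hour window. Since spirometry is not the sample-size outcome, this is a minor-to-moderate point.

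**What to change.** For daily spirometry, replace repeated measures ANOVA in the SAP with a likelihood-based linear mixed model in SAS using all observed values. Include arm, day, arm-by-day, the baseline spirometry already collected, and baseline-by-day. Test the arm contrast at prespecified early postoperative days, for example days 1 and 2. A simpler acceptable alternative is a baseline-adjusted comparison at one fixed early day, before most discharges. A sensitivity analysis that shifts the missing post-discharge values is optional.

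The cost is a few lines of SAP text and a little more analysis work in software already planned, with no new data, visits or patients. The single-day option gives up some power (86% against 91-95% under the assumptions above). The mixed model is unbiased only if discharge depends on recorded values. If it depends on the same day's unrecorded score, a true 0.50 SD is estimated at 0.46, 0.43 and 0.41 under the three sharp thresholds. With no true effect and an arm-specific rule, the estimates are −0.04, −0.07 and −0.09.
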